The simplest formula for the sample size calculation were identified through continuous outcome and equal sample sizes in both groups yields (Noordzij et al., 2010), which primary outcome of this study, a priori between-group difference at 5 months with cognitive performance, BACS composite score. A difference in cognitive function of 30.6 between the treated and control group $(\mu 1-\mu 2)$ with the SD of 49.9 (Rodríguez-Sánchez, Crespo-Facorro, González-Blanch, Perez-Iglesias, & Vázquez-Barquero, 2007) is considered as clinically relevant and specified such an effect to be detected with power of 80% power (0.80) and a two-sided alpha of 0.05 and beta of 0.20. This requires 42 participants to be randomised to each arm. Assuming 20% of attrition rate, the adjusted sample size will be involved in this intervention programme is 52 participants each arm with 104 participants in total for achieving desired statistical significance for a given hypothesis.

Inclusion Criteria

The inclusion criteria is established to recruit clinically stable participants according to DSM-V criteria for schizophrenia, schizophreniform disorder or schizoaffective disorder as diagnosis and presenting with cognitive deficits of young adults between 18 to 40 years. They will be provided a written informed consent and fulfil the criteria of cognitive measures, symptomatology and other functioning which to be considered as participants in this study. Moreover, they should be able to understand and/or speak a Malay language, read and write in Malay and/or English as well as able to give informed consent as considerations for being a participant in this study.

Exclusion Criteria

Participant can be excluded if they have previous diagnosis of mental retardation, psychotic disorder related to a general medical conditions or substance-induced psychotic disorder as well as concurrently undergo other types of CRT. The participation in the study is voluntary and

participants are free to withdraw from the study at any time for any reason without consequences for treatment possibilities. The researcher may decide to terminate the study at any time. Participants will be informed if the study is terminated and follow-up visits will be arranged if needed. They may also be withdrawn from the study at any time at the discretion of the researcher.

Measures and Instruments

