the domains of verbal memory (list learning), working memory (digit sequencing task), processing speed (verbal fluency, token motor task, symbol coding), and executive functions/ reasoning and problem solving (Tower of London). As the BACS Malay version (BACS-M) was validated in both clinical and healthy groups in Malaysia, the likelihood of treatment-related effect with high test-retest reliability in the composite score are considered in this study for assessing cognitive change. It has proven promising useful tool with good test-retest reliability ICCs of 0.89 and required a mean of 39.27 min to complete which consistent with the original English version of the BACS that required less than 35 minutes to be completed (Keefe et al., 2006). It may aid the evaluation of cognitive within 2 weeks between assessments and before remediation strategies could be conducted. Trained psychologists to participants and controls will carry it out to the local participants.

Functional Assessments

In addition, improvement in a co-primary measure of either functional capacity or an interviewbased measure of cognitive functioning was also specifically recommended (Buchanan et al., 2005, 2010). The Schizophrenia Cognition Rating Scale (SCoRS) is an interview-based measure of cognitive functioning. The relationship between real world functioning and performance on three measures of functional capacity will be measured including SCoRS, Social Functioning Scale (SFS), and Schizophrenia Quality of Life Scale Revision 4 (SQLS-R4).

Schizophrenia Cognition Rating Scale (SCoRS)

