The descriptive statistics will be used to report the participants in terms of demographic and clinical data as well as inferential analysis such as t-test analysis for mean score of the post test. Hence, the Independent Sample t-tests will be used to compare participants and controls on age, years of education and premorbid IQ. The chi-square (χ 2) test will be used to compare the difference between groups in demographic characteristics. The relationship among the BACS measures will be evaluated through Pearson correlations among the composite scores by averaging all z-scores of the six primary measures. Pearson correlation for reliability and repeated measures for the validity of the test. The mixed model one-way analysis of variance (ANOVA) between and within group of intervention is expected to compare the difference between the means of pre and post treatment. The group differences on cognitive performance then analysed by the multivariate analysis of variance (MANOVA). The treatment effect on symptom and functioning outcomes will be analysed using Multiple Linear Regression (MLR) analysis. Effect sizes of the improvement in cognitive domain and psychosocial functioning will

also be calculated. The data analyses will be done using the SPSS version 22. All available data who met entry criteria will be analysed, which provided all outcomes on an intention to treat analysis (ITT) approach, assuming data which missing at random, including any significant predictors (Anaya et al., 2012).

Ethical Consideration

This study will be conducted in compliance with ethical principles outlined in the Declaration of Helsinki and Malaysian Good Clinical Practice Guideline. All potential participants will be enrolled in the study of cognitive remediation for first episode psychosis as defined in inclusion criteria. As the study involves UKM Medical Centre and government hospitals such as Kuala Lumpur Hospital, Kajang Hospital and Putrajaya Hospital, hence the approval from Ethics Committee of UKM and Ministry of Health (MOH) Malaysia ethical board (NMRR) have been obtained.

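### Three overlapping tests are named for cognition, none is designated primary and none is stated as baseline-adjusted; one ANCOVA of the BACS-M composite would be more precise at no extra cost

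*Protocol*

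**What the plan says.** The Statistical Analysis section of the Protocol names three procedures that could carry the comparison of the arms on cognition:

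- a "t-test analysis for mean score of the post test", with no outcome or visit named;
- "The mixed model one-way analysis of variance (ANOVA) between and within group of intervention", to compare means before and after treatment;
- "The group differences on cognitive performance then analysed by the multivariate analysis of variance (MANOVA", with no list of dependent variables.

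None is called primary. Multiple linear regression is reserved for symptoms and functioning, and its covariates are not listed.

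The Sample size calculation section, in contrast, is specific. It sizes the trial on the "a priori between-group difference at 5 months with cognitive performance, BACS composite score". The inputs are "A difference in cognitive function of 30.6 between the treated and control group", "with the SD of 49.9" and "power of 80% power (0.80) and a two-sided alpha of 0.05 and beta of 0.20". The result is 42 per arm, raised to 52 for 20% attrition. No baseline correlation enters.

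Baseline BACS-M is collected from everyone before randomisation (Measures and Instruments; Baseline measures). The BACS section reports "good test-retest reliability ICCs of 0.89" and mentions two weeks between assessments. It gives no correlation over 8 weeks or 5 months.

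**The concern.** The hypothesis is superiority of ReMind over conventional NEAR, and the sample size is tied to one quantity, the composite at 5 months. The analysis section does not tie itself to that quantity. Its three procedures ask different questions:

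- The post-test t-test compares the arms but leaves all stable between-patient variation in the error term.
- The mixed ANOVA contains several contrasts. The pre-versus-post contrast is not a treatment comparison: both arms receive active cognitive remediation, so it mixes practice, recovery and whatever the two programmes share. The group main effect averages in a baseline that treatment cannot have affected. Only group-by-time isolates ReMind against standard remediation, and it is not named.
- The MANOVA is an omnibus test against any pattern of differences. A significant result need not mean that the composite is better under ReMind.

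At stake is which result counts if the three disagree, and the precision lost in a small trial by not using a covariate that is already collected.

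**Working it through.** **Inputs.** From Sample size calculation: difference 30.6, SD 49.9, two-sided alpha 0.05, power 80%, equal arms, 42 per arm before attrition. Standardised difference: 30.6 / 49.9 = 0.613. Assumed: baseline-to-outcome correlation r from 0.5 to 0.8, with 0.3 and 0.4 as lower checks, and equal variances at the two visits.

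**The plan's own figure.** n per arm = 2 × [49.9 × (1.960 + 0.842) / 30.6]² = 41.7, rounded up to 42. The stated figure reproduces, and the formula is that of an unadjusted comparison of two means.

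**Post-test t-test on the composite.** Power at 42 per arm is 80.2% by the normal approximation and 79.3% by the noncentral t. If all 52 per arm contribute, it is 87% to 88%.

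**ANCOVA on baseline.** The error variance is multiplied by 1 − r², so the unadjusted test gives up a share r² of the ANCOVA precision.

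**Group-by-time in a pre/post ANOVA.** This equals a t-test on change scores, with variance factor 2(1 − r). Efficiency relative to ANCOVA is (1 − r²) / [2(1 − r)] = (1 + r) / 2.

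Both powers below are at 42 per arm and a difference of 30.6, by the noncentral t.

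| r (assumed) | Precision given up by t-test, r² | ANCOVA power | Group-by-time efficiency, (1 + r)/2 | Group-by-time power |
|---|---|---|---|---|
| 0.3 | 9% | 83% | 65% | 65% |
| 0.4 | 16% | 86% | 70% | 72% |
| 0.5 | 25% | 89% | 75% | 79% |
| 0.6 | 36% | 93% | 80% | 87% |
| 0.7 | 49% | 97% | 85% | 95% |
| 0.8 | 64% | over 99% | 90% | 99% |

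At r = 0.5 the change-score variance factor is 2 × 0.5 = 1, so group-by-time has exactly the power of the post-test t-test. Below that it does worse.

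**MANOVA.** Assume the dependent variables are the six BACS subtests. With two groups the test is Hotelling's T², with 6 and 84 − 6 − 1 = 77 degrees of freedom and noncentrality (42/2) × D².

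- Composite effect of 0.613 SD spread evenly over six equally correlated subtests: D² = 0.613² = 0.376, noncentrality 21 × 0.376 = 7.9, power 49%. At 52 per arm it is 60%; 76 per arm would be needed for 80%.
- Same composite effect confined to the three processing-speed subtests (verbal fluency, token motor, symbol coding): with assumed inter-subtest correlations of 0.2 to 0.6, D² is 1.32 to 4.14 and power is 98% or more.

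**The case against.** The strongest reply is that the plan does not fail on its own terms. The sample size was computed for an unadjusted two-mean comparison, the t-test is that comparison, and under randomisation it is valid. A separate analysis plan may also exist that names the primary test and the interaction. The first part stands. The second would settle the matter if such a plan does so, but this Protocol already lists the procedures and leaves them unranked.

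Three stronger readings are tempting, and the documents do not support them.

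- A reader might infer that the planned analyses fall short of the stated 80% power. The t-test does not. Group-by-time does so only if r is below about 0.5, and the MANOVA only under some effect patterns.
- A reader might infer from the ICC of 0.89 that most of the available precision is thrown away. For the t-test that needs r above about 0.71 (0.71² ≈ 0.50). The 0.89 is a short-interval reliability and no 5-month correlation is given. The mixed ANOVA, moreover, does use baseline through group-by-time.
- A reader might take 49% as the power of the MANOVA. Six dependent variables is an inference, since the six measures are mentioned for the composite. An even spread is also the least favourable pattern for a fixed composite effect with equal correlations, and this intervention targets processing speed.

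Some wording could also be read more kindly. The t-test sentence names no outcome, and the next one applies t-tests to age, education and premorbid IQ. The MANOVA may be meant as a later step. The intention-to-treat sentence allows for significant predictors, but that is too vague to count as adjustment for baseline BACS-M.

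**Conclusion.** The point holds as one of specification and efficiency. The Protocol designates no primary test for cognition, does not identify the treatment contrast within the ANOVA, and states no baseline-adjusted model for the composite on which it sized the trial.

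For r between 0.5 and 0.8, the unadjusted t-test gives up 25% to 64% of ANCOVA's precision and group-by-time gives up 10% to 25%. At the planned difference and 42 per arm, power would rise from about 80% with the t-test to between 89% and over 99% with ANCOVA.

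These sizes rest on assumed correlations and on the Protocol's own difference and SD. The gain in precision is present at any nonzero r, but at r = 0.3 it is only 9%. The MANOVA figures rest further on an assumed set of dependent variables and effect pattern. They show that its power is not assured by the sample size, not that it is low.

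**What to change.** Name one primary analysis: an ANCOVA, or equivalent linear model, of the BACS-M composite at 5 months on arm and baseline BACS-M composite, reporting the adjusted mean difference with its 95% confidence interval. State that the post-test t-test, the mixed ANOVA (with group-by-time as its treatment contrast) and the MANOVA (with its dependent variables listed) are supportive or descriptive. Include the baseline value of each outcome in the planned regressions for PANSS, SCoRS, SFS and SQLS-R4. Adjustment for hospital is optional, since no stratification by site is described.

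The cost is a change of wording. Baseline is already measured, the sample size can stay as it is, and SPSS 22 fits the model.

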The SQLS-R4 a fourth revision of the original SQLS developed by Wilkinson and colleagues in 2000. It measures two domains of psychosocial feelings, and cognition and vitality in individuals with a diagnosis of schizophrenia. It can be applied in clinical research and any publication due to its impressive measurement characteristics of this tool. In this study, the SQLS-R4 which has already translated into Malay version will be used to the respondents (Taha, Ibrahim, Rahman, Shafie, & Rahman, 2012).

Outcome measures

The trial involves the most effective treatment to enhance the outcomes in the early stages of psychosis with the primary aim to improve the long-term cognitive functioning.

Baseline measures

[figure not shown]
All inclusion criteria must be met before continuing neuropsychological assessment of the BACS-M to measure the primary outcome of cognitive functioning, PANSS which will be used to assess symptomatology and psychopathology of participants, SCoRS for functional capacity, SQLS-R4, and SFS for secondary outcomes of psychosocial functions.

Study Procedure

The study will involve multidisciplinary team, which covers from assessment, interview, randomisation and intervention. The CR training will be required team of trained clinicians

including Clinical Psychologists with at least a master's degree, Psychiatrists, Occupational Therapists, and Nurses as the recruitment and training team. In fact, the person involved in this study have been provided with a 2-day training on CR and its process to ensure the fidelity of treatment will be sustained with thorough supervision. All the assessments and interview will be administered prior to randomisation into intervention programme and immediately after intervention. It followed by interview sessions of psychopathology, psychosocial and quality of life to participants. The three months follow up is considered after termination prior to study analysis as shown in the diagram.

Consolidated Standards of Reporting Trials (CONSORT) flow diagram of participants through each stage of a randomized trial.

ReMind Cognitive Training

The intervention consists of 15 sessions with the selected web based computerised cognitive training associated with homework between each session. In this program, the therapy intensity involved 2 sessions per week for 8 weeks with 15 hours to deliver an adequate treatment to improve cognitive functioning (McGurk et al., 2007a).

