It is important to demonstrate that the project has been completed within the time allocated. Timeline considers all phases of the project including conducting a literature review, obtaining ethical clearance, writing up results and final reports.

Acknowledgements

The study has been registered through the National Medical Research Register (NMRR-16-598-29797) and Trial Registration (ISRCTN17220814). The approval to conduct the program was obtained from the Ethics Committee of Universiti Kebangsaan Malaysia (NN-2016-037) and the Ministry of Health (MOH) through the Medical Research Ethics Committee (MREC). The funding for the study grant was provided by the Centre for Research and Instrumentation (CRIM), Universiti Kebangsaan Malaysia through Geran Galakan Penyelidikan (GGP-2017-062). The data findings described in the manuscript is fully accessible without restriction, with rare exception.

Competing interests

There is no potential conflict of interest in relation to this article.

GANTT CHART FOR PhD COMPLETION

TASK TO BE PERFORMED/ YEAR		2015/2016 SEM 1					2015/2016 SEM 2						2016/2017 SEM 3						2016/2017 SEM 4					2017/2018 SEM 5					2017/2018 SEM 6					2018/2019 SEM 7			
	9	1 0	1 1	1 2	1 2	3	4	5	6		7 8	9) (1 0		1 2	1 2	3	4	5	67	7 8	9	1 0	1 1	1 2	1	2	3 4	1 5	6	7 8	9	1 0	1 1	1 1 2	2
Identify Research Area/ Problem identification																																					
Analysis & Justification																																					
Literature review																																					
Developing objectives and hypotheses																																					
Choose variable																																					
Choose type of study & sampling technique																																					
Formulate Research (questions, design & strategy) and select methods																																					
Write research proposal																																					
Negotiate access																																					
Submit proposal																																					
Defence Proposal																																					
Ethical consideration																																					
Applying research grant/ fund																																					
Pre-testing (Pilot Study) & Sampling																																					
Preparing 1 st journal publication																																					
Validation study/ NEAR software development																																					
Data collection																																					

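### Statistical Analysis assigns repeated measures to validity and Pearson correlation to reliability: the first gives no evidence of validity and the second misses systematic shift (a minor, ancillary error)

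*Protocol*

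**What the plan says.** The Statistical Analysis section of the protocol plans "Pearson correlation for reliability and repeated measures for the validity of the test". It does not name the test. The sentence just before it reads "The relationship among the BACS measures will be evaluated through Pearson correlations among the composite scores by averaging all z-scores of the six primary measures", so the BACS is the natural referent. Under Baseline measures the protocol uses the "BACS-M to measure the primary outcome of cognitive functioning".

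The BACS section gives the grounds for choosing the instrument: "As the BACS Malay version (BACS-M) was validated in both clinical and healthy groups in Malaysia", with "good test-retest reliability ICCs of 0.89". It adds: "It may aid the evaluation of cognitive within 2 weeks between assessments and before remediation strategies could be conducted".

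Under Study Procedure, assessments are "administered prior to randomisation into intervention programme and immediately after intervention", and a follow-up comes three months later. Under Study design, both arms receive cognitive remediation, the control arm as standard CRT. The Gantt chart has a row "Validation study/ NEAR software development" directly above the data collection row.

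The protocol gives no data set, time points, threshold, null hypothesis or decision for the reliability and validity analysis.

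**The concern.** Each method is paired with a property that it does not measure, or measures only in part.

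- **Validity.** Whether a test measures cognition is judged against something outside the test, such as a criterion measure or known groups. A repeated-measures analysis compares the test's mean with itself at another time. It addresses change, and at most responsiveness.
- **Reliability.** Pearson's r describes linear association between two sittings. If every participant gains the same amount on the second sitting, for instance through practice, r does not move although the scores no longer agree.
- **Data source.** If the repeat scores are those taken after the intervention, every participant has been assigned to cognitive remediation in between. Retest correlation and mean change would then contain treatment response as well as measurement error, whichever coefficient is used.

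At stake is any statement in the trial report that the BACS-M proved reliable or valid in this sample. The stated methods could not carry a validity statement, and would carry a reliability statement only in part.

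**Working it through.** **Inputs.** The protocol gives no figure for this analysis, so there is none to reproduce. The sample sizes below come from Sample size calculation: 42 per arm (84 in all) before attrition, and 104 in total. The 42 reproduces: 2 × (1.960 + 0.842)² × 49.9² / 30.6² = 41.7, rounded up to 42. The retest value 0.89 is the cited ICC, borrowed here as a value for r. All shifts between sittings are assumed. One of them, 0.41 SD, is the size of the meta-analytic effect of cognitive remediation on global cognition quoted in the background; it is a treatment effect, not an observed retest shift.

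**1. Pearson's r against agreement.** Take two sittings with unit variance, correlation r and a uniform shift of d SD. The variance components are r between subjects, d²/2 between occasions and 1 − r residual. Hence

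ICC (absolute agreement) = r / (r + d²/2 + 1 − r) = r / (1 + d²/2).

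| Shift d (SD, assumed) | Pearson r | Absolute-agreement ICC |
|---|---|---|
| 0 | 0.89 | 0.89 |
| 0.3 | 0.89 | 0.89/1.045 = 0.85 |
| 0.41 | 0.89 | 0.89/1.084 = 0.82 |
| 0.5 | 0.89 | 0.89/1.125 = 0.79 |
| 1.0 | 0.89 | 0.89/1.5 = 0.59 |

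With no shift the two indices coincide. A consistency ICC, r / (r + 1 − r) = r, would ignore the shift just as Pearson's r does.

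**2. Repeated measures as a validity check.** For two occasions the analysis is a paired comparison with noncentrality d√n / √(2(1 − r)). At n = 84 and two-sided 0.05:

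| Retest r | Shift d (SD) | Noncentrality | Probability of rejecting equal means |
|---|---|---|---|
| 0 (pure noise) | 0.2 | 1.30 | 25% |
| 0 (pure noise) | 0.41 | 0.41 × 9.165 / 1.414 = 2.66 | 75% |
| 0.30 | 0 | 0 | 5% |
| 0.30 | 0.5 | 0.5 × 9.165 / 1.183 = 3.87 | 97% |
| 0.89 | 0 | 0 | 5% |

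At n = 104 the 97% becomes 99%. With no shift, an unreliable and a reliable instrument both reject 5% of the time. With a shift, an instrument that is pure noise can reject often. Nothing in the calculation refers to a quantity outside the test, so neither outcome bears on validity.

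**3. Where repeat data could come from.** Study Procedure places the repeat assessment after the intervention, and a follow-up three months later. The BACS section mentions a two-week interval before remediation, and the Gantt chart lists a validation study. The analysis sentence refers to neither. Mixing with treatment response therefore follows only if the post-intervention visits are used.

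**The case against.** The strongest reply is that this is an ancillary sentence with no consequence for the trial. The BACS-M was chosen on an existing Malaysian validation, the objectives contain no psychometric aim, and no eligibility rule, endpoint or treatment comparison waits on the result. That stands, and it limits the point to a minor one.

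Several stronger readings are tempting, and the documents do not support them:

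- *That the instrument would be passed or failed by a significance test.* A Pearson test of zero correlation is significant from about r = 0.215 at n = 84, or 0.193 at n = 104. But the protocol states no null hypothesis or p-value rule, and r may simply be reported as a coefficient.
- *That Pearson's r has nothing to do with reliability.* It is a recognised retest index, and the formula above moves with it. The defect is only that it omits shift.
- *That almost any data would appear to support the BACS-M.* If rejection counted as support, a stable test with r = 0.89 would gain it 5% of the time. The method is uninformative, not lenient.
- *That the reliability figure would be overstated against the cited 0.89.* The protocol does not give the form of that ICC. If it measures consistency, it equals Pearson's r under equal variances.
- *That the results are confounded by treatment.* The two-week interval and the validation study leave room for a retest before treatment.
- *That an unsound primary instrument could be declared sound.* The protocol rests the choice of instrument on the earlier validation, not on this check.

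The sentence may also have been carried over from the validation study. Even so, it stands unlabelled among the trial analyses, and repeated measures would not establish validity there either.

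**Conclusion.** The point holds as a minor mismatch between method and purpose. The validity half is wrong on any reading: a comparison of means over time gives no evidence of validity. The reliability half is incomplete: Pearson's r misses systematic shift, which at r = 0.89 would be a difference of 0.07 from the absolute-agreement ICC for an assumed shift of 0.41 SD (0.89 against 0.82), and none if there is no shift. Mixing with treatment response is conditional on use of the post-intervention visits.

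The conclusion assumes that the test in question is the BACS; the numerical illustration assumes equal variances and shifts that the protocol does not supply. The primary treatment comparison is unaffected.

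**What to change.** Either of two changes is enough.

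1. Delete the sentence and rely on the BACS-M validation already cited in the BACS section (ICC 0.89), with no reliability or validity claim from this trial.
2. If a repeat administration before remediation exists, replace the sentence with wording such as: Test-retest reliability of the BACS-M will be estimated by a two-way absolute-agreement ICC with 95% CI, using only repeat administrations completed before remediation starts; repeated-measures analyses will be used only for change over time.

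Any validity statement should rest on an external criterion. The baseline correlation of the BACS-M composite with the SCoRS global rating, with 95% CI, would serve and uses data already planned. It is optional, since the objectives include no such aim.

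If the sentence belongs to the separate validation study, it should be moved there or labelled, and its validity part still corrected.

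The cost is one sentence of analysis text, with no new visits, data or participants. The downside is that the reported reliability may be lower than a Pearson r, or that no reliability claim can be made from this trial.
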